Title: A randomized sham-controlled double-masked Phase 2a study of the efficacy, safety and tolerability of the intravitreal plasma kallikrein inhibitor, KVD001, in subjects with center-involving diabetic macular edema (ciDME) who have had prior anti-vascular endothelial growth factor (VEGF) treatment.

All documentation for this study that is supplied to me and that has not been previously published will be kept in the strictest confidence. This documentation includes this study protocol, Investigator's Brochure (IB), electronic case report form (eCRF), and other scientific data.

The study will not be commenced without the prior written approval of a properly constituted Institutional Review Board (IRB) and/or Independent Ethics Committee (IEC). No changes will be made to the study protocol without the prior written approval of the Sponsor and the IRB and/or IEC, except where necessary to eliminate an immediate hazard to the patients.

I have read and understood and agree to abide by all the conditions and instructions contained in this protocol.

I agree and understand that as the Principal Investigator, it is my responsibility to train my staff on all updates to the clinical protocol, and to ensure that such training is acknowledged in the appropriate study documentation.

Responsible Investigator of the local study center

Signature

Date

Name (block letters)

Title (block letters)

Institution (block letters)

Phone number

PROTOCOL SYNOPSIS

Title	A randomized sham-controlled double-masked Phase 2a study of the efficacy, safety and tolerability of the intravitreal plasma kallikrein inhibitor, KVD001, in subjects with center-involving diabetic macular edema (ciDME) who have had prior anti-vascular endothelial growth factor (VEGF) treatment
Sponsor Study No.	KVD001-201
Phase	2a
Sponsor	KalVista Pharmaceuticals, Ltd.
Study Center(s)	Ophthalmology clinics in the United States (US) with experience in the conduct of diabetic macular edema (DME) clinical studies
Objective(s)	
Primary Objective:
 
 • To evaluate the efficacy of monthly dosing of intravitreal (IVT) injection of KVD001 in subjects with ciDME who have had prior anti-VEGF treatment 
Secondary Objective:
 
 • To evaluate the local and systemic safety and tolerability of monthly dosing of KVD001 Injection in subjects with ciDME who have had prior anti-VEGF treatment
Design	
This is a phase 2a, randomized, double-masked, sham-controlled, 3-arm study to evaluate the efficacy, safety, and tolerability of KVD001 Injection as monotherapy in adult subjects with ciDME who have had prior anti-VEGF treatment. Approximately 123 eligible subjects will be randomized into the study.
 
The maximum duration of the study for each randomized subject will be up to 28 weeks (including up to 4 weeks for screening, 12 weeks treatment period, and 12 weeks follow-up).
 
The study will be conducted on an out-patient basis.
 
The study schedule of events will be as follows:
 
Screening Phase: The screening period will be up to 4 weeks. All subjects will sign an Informed Consent Form (ICF) prior to any study related procedures being performed. Subjects will be 18 years of age or older, at the time of screening, and will have a diagnosis of ciDME with prior anti-VEGF treatment.
 
Treatment Phase: On the day of first study drug administration (Day 1), the subject's eligibility will be reconfirmed and baseline assessments will be performed. Eligible subjects will be randomized 1:1:1 to receive KVD001 Injection (6 µg or 3 µg KVD001) or a sham procedure during a 12-week, double-masked treatment period (a total of 4 doses given at approximately monthly intervals).
 
Subjects will visit the study clinic on Day 1 and Weeks 4, 8, and 12 during the Treatment Phase for study drug administration or sham procedure, safety, and ophthalmic assessments (see

	
Table 2). The subject will remain in the clinic after study drug administration or sham procedure until all post-dose procedures and observations have been completed and the Investigator confirms that the subject may be discharged. Investigators should schedule visits at Week 4, 8, and 12 to provide 28 days between visits. The visit window for these visits is -3 days to +7 days.
 
Approximately twenty-four (24) hours after each study drug administration or sham procedure on Day 1 and Weeks 4, 8, and 12, subjects will be contacted by telephone to evaluate any reported adverse events (AEs) and changes in concomitant medications. In the event of any reported ocular or systemic AEs that are considered by the Investigator to be a possible cause for concern, the subjects will return to the clinic for assessment as soon as possible.
 
Follow up Phase: All subjects will visit the clinic at Weeks 16, 20, and 24 after the last study drug administration or sham procedure for safety and ophthalmic assessments (see Table 2). The visit window for Weeks 16, 20, and 24 is ± 7 days.
 
Early Discontinuation: If any subject discontinues the trial early, every effort should be made to complete the Week 24/early discontinuation (ED) evaluations as soon as possible and, whenever possible, prior to starting any new medication or treatment. All attempts will be made to not discontinue the subject unless necessary.
 
Rescue Treatment: Rescue intervention (e.g., anti-VEGF, focal/grid macular laser photocoagulation, (IVT) steroids) may be administered due to worsening DME (i.e., attributable to worsening DME and not another cause;) if either of the following occurs and, where possible, after consultation with the Medical Monitor:
 
 • During Treatment Phase 
 ○ Best corrected visual acuity (BCVA) deteriorates 3 lines (15 letters) or more from baseline ○ Central Subfield Thickness (CST) worsening of $>100 \mu\text{m}$ from baseline • During Follow up Phase (i.e., after week 16) 
 ○ BCVA deteriorates 3 lines (15 letters) or more from highest BCVA during treatment phase or baseline ○ CST worsening of $>100 \mu\text{m}$ from lowest CST during treatment phase or baseline. 
Subjects who receive a rescue intervention in the study eye will be discontinued from further study participation.


Investigational Product
	
KVD001 Injection consists of KVD001 (as hydrochloride [HCl] salt), trehalose dihydrate, histidine, and water for injection. KVD001.HCl will be supplied in 2 mL glass vials at the

	
concentration of 60 µg/mL and 30 µg/mL KVD001. KVD001 Injection is 6 µg or 3 µg KVD001 administered as a 100 µL volume IVT injection.

Number of Subjects	
Approximately 123 eligible subjects will be randomized into this study.

Population	
The study population will include male and female subjects 18 years of age or older with ciDME who have received prior anti-VEGF treatment.
 
Except as otherwise defined, subjects must fulfill all of the following criteria both at Screening and on Day 1 to be eligible for inclusion in the study. For applicable conditions, subjects who do not meet the inclusion criteria at Visit 1 or 2 may be rescreened with permission from the Sponsor or Ora.
 
The study eye will be defined as the eye that meets all of the inclusion and none of the exclusion criteria. If both eyes qualify, the eye with the worse BCVA ETDRS at Day 1 will be used as the study eye. If both eyes have the same BCVA ETDRS at Day 1, the eye with the highest CST on spectral-domain optical coherence tomography (SD-OCT) on Day 1, as assessed by the Investigator, will be used as the study eye. If both eyes qualify and neither is preferred based on the inclusion/exclusion criteria and have the same BCVA ETDRS and CST on Day 1, either eye may be chosen as the study eye. In this instance, the Investigator should select the eye that, in their opinion, is most likely to respond to treatment as the study eye.
 
Inclusion Criteria:
 
 1. Male or female adult subjects 18 years of age and older. 2. Confirmed diagnosis of Type I or Type II diabetes mellitus (DM). Any of the following are sufficient: 
 ○ Current regular use of insulin for the treatment of diabetes ○ Current regular use of oral anti-hyperglycemia agents for the treatment of diabetes ○ Documented diabetes by American Diabetes Association and/or World Health Organization (WHO) criteria 3. BCVA, using Standard Early Treatment Diabetic Retinopathy Study (ETDRS) chart, of ≥19 letters (~20/400) and ≤73 letters (~20/40) in the study eye and ≥34 letters (~20/200 or better) in the fellow eye at Screening and Day 1. 4. Presence of ciDME in the study eye defined as Heidelberg Spectralis Optical Coherence Tomography (SD-OCT) CST ≥305 µm in women and ≥320 µm in men in the study eye (as assessed at Screening by the Investigator and Central Image Reading Center (CIRC) and on Day 1 by the Investigator). 5. Subjects' first anti-VEGF injection in the study eye occurred ≤36 months prior to Day 1. 6. Subjects have received at least 3 anti-VEGF injections in the study eye within a 6-month period within the 36 months prior

	
to Day 1.
 
 7. The last anti-VEGF injection in the study eye is ≥ 8 weeks prior to Day 1. 8. Subjects, who in the view of the Investigator, are able to defer treatment in the study eye for at least 6 months following Day 1. Note, rescue treatment is available (see Section 5.8). 9. Values for blood and urine safety labs at the Screening visit showing no clinically significant deviation as determined by the Investigator. 10. Women who are post menopausal for at least 1 year, surgically sterile for at least 3 months prior to Day 1, or who are agreeable to using highly effective contraception (adequate contraceptive measures include stable use of oral contraceptives or other prescription pharmaceutical contraceptives for two or more menstrual cycles prior to screening; intrauterine device (IUD); bilateral tubal ligation; vasectomy; condom plus contraceptive sponge, foam, or jelly or diaphragm plus contraceptive sponge, foam, or jelly), or abstinence. 11. Sexually active men who are not vasectomized and have sexual partners of childbearing potential should be agreeable to using highly effective contraception. 12. Provide signed informed consent and are willing and capable of complying with clinic visits and study procedures.
	
Exclusion Criteria:
 
 1. Females who are pregnant or lactating, or expecting to become pregnant during the course of the study. 2. Evidence of ocular pathology (e.g. visually significant cataract) that impacts subject's vision in the study eye from any cause other than DME, in the opinion of the Investigator. 3. Evidence/presence of amblyopia, vitreomacular traction, epiretinal membrane, foveal atrophy, or foveal ischemia, or any other condition in the macula that is thought to impair the subject's vision (other than DME) in the opinion of Investigator. 4. Prior treatment with panretinal photocoagulation or focal grid macular photocoagulation in the study eye within the previous 3 months prior to Day 1. 5. Prior treatment with IVT steroid in the study eye (in the 3 months prior to Day 1 for triamcinolone, 6 months prior to Day 1 for Ozurdex and at any time for Iluvien). 6. Prior treatment with topical NSAIDs or topical steroids in the study eye within 1 month prior to Day 1. 7. Prior treatment with Jetrea® (ocriplasmin) injection in the study eye within the previous 3 months prior to Day 1.

8. Prior treatment with systemic corticosteroids or systemic anti-VEGF therapy within 3 months prior to Day 1.
9. Prior vitrectomy in the study eye.
10. Prior intraocular surgery in the study eye except for cataract surgery. Cataract surgery within the previous 6 months of Day 1 in the study eye is excluded.
11. Intraocular pressure (IOP) at Screening or Day 1 of >22 mmHg in the study eye or use of >2 antiglaucoma agents (combination agents count as 2 agents) in the study eye.
12. Evidence of infectious dacryocystitis, significant blepharitis, active conjunctivitis, infectious keratitis, or scleritis in either eye, or any other condition that might affect the safety of the IVT injection in the opinion of Investigator.
13. Evidence of active intraocular inflammation in the study eye.
14. Current active proliferative diabetic retinopathy (PDR), active anterior segment neovascularization (ASNV), active retinal neovascularization, or the presence of vitreous hemorrhage in the study eye. (Note, quiescent PDR is not exclusionary).
15. Any concurrent ocular condition in the study eye which, in the opinion of the Investigator, could interfere with the evaluation of efficacy or safety.
16. Poorly controlled DM defined as glycosylated hemoglobin [HgA1c] $\geq 12.0\%$ or having initiated intensive insulin treatment (a pump or multiple daily injections) within prior 4 months or planning to do so in the next 2 months, or two (2) or more episodes of diabetic ketoacidosis requiring hospitalization within the preceding 6 months.
17. Uncontrolled hypertension at Screening or Day 1 defined as systolic ≥ 180 mmHg or diastolic ≥ 110 mmHg.
18. Significant co-existing disease such as marked hepatic impairment, end stage renal disease (defined as a current or imminent requirement for dialysis), symptomatic cardiac failure, or significant pulmonary dysfunction that may place the subject at higher risk for treatment complications, failure of follow-up, and/or may impact the outcome of the data interpretation of the study, in the opinion of the Investigator.
19. History of other disease (e.g., unstable psychiatric illness), metabolic dysfunction, physical examination finding, or clinical laboratory finding giving reasonable suspicion of a disease or condition that contraindicates the use of an investigational product, might affect interpretation of the results of the study, or renders the subject at high risk for treatment complications or lack of follow-up, in the opinion of Investigator.
20. History of alcohol and/or drug abuse in the last 2 years.
21. Participation in an interventional investigational clinical study

	
within 3 months or within 5 half-lives of the last dosing of investigational drug (whichever is longer) prior to Screening.
 
22. Inadequate media clarity or pupillary dilation that does not allow acquisition of an adequate quality OCT and/or fundus image.

Criteria for Evaluation of Efficacy	
Primary Efficacy Endpoints:
 
 Change from baseline in BCVA letter count as measured by ETDRS at Week 16 
Secondary Efficacy Endpoints
 
 Change from baseline in CST as measured by Spectral Domain OCT (SD-OCT) Proportion of eyes with a ≥ 2 step improvement from baseline in Diabetic Retinopathy Severity Scale (DRSS) score Change from baseline in BCVA letter count as measured by ETDRS at Weeks 4, 8, 12, 20 and 24 Proportion of study eyes with ≥ 5, ≥ 10, and ≥ 15 BCVA letter change from baseline (gain and loss)
Efficacy Variables	
 BCVA in letters as measured by ETDRS CST in μm as measured by Spectral Domain (SD)-OCT Retinopathy severity as measured by the DRSS and graded from fundus photography
Safety Variables	
 AEs Ophthalmic and physical exam findings Laboratory test results (clinical chemistry, hematology, and urinalysis) Vital signs (systolic blood pressure [SBP], diastolic blood pressure [DBP], pulse rate (PR), and respiratory rate)
General Statistical Methods and Types of Analyses	
Analysis Populations:
 
 Full Analysis Set (FAS) – All randomized subjects following the principle of intention-to-treat (ITT). Subjects will be included in the analysis according to the treatment to which they were randomized. Per Protocol Set (PPS) – All randomized subjects who are compliant with the study protocol, i.e., who do not experience any major protocol deviations. Subjects will be included in the analysis according to the treatment received. Safety Set (SAF) – All randomized subjects who receive at least one dose of study treatment. Subjects will be included in the analysis according to the treatment received. 
Sample Size: The proposed sample size (41 per treatment group) will provide

	
approximately 80% power to detect a difference in change from baseline of 5 letters between either of the KVD001 treatment groups and sham based on a two-sided, two-sample t-test with significance level 0.05 and assuming a pooled standard deviation (SD) of 7.5 letters.
 
Multiplicity Considerations:
 
No multiplicity adjustments are planned in this exploratory Phase 2a study.
 
Primary Efficacy Analyses:
 
The primary efficacy endpoint is the change from baseline in BCVA letter count in the study eye at Week 16. Change from baseline in BCVA letter count will be calculated as Week 16 BCVA letter count minus Day 1 BCVA letter count such that a negative difference indicates a worsening in vision. In addition, treatment comparisons between each dose of the KVD001 Injection and the sham procedure will be calculated as KVD001 Injection minus sham, such that a positive result indicates more letters gained in the KVD001 Injection treatment group.
 
The study eye ETDRS letter scores including changes from baseline will be summarized using continuous descriptive statistics. An analysis of covariance (ANCOVA) model will be used to compare the change from Day 1 in BCVA letter count at Week 16 between each dose of the KVD001 Injection and the sham. The ANCOVA model will include treatment as a main effect and baseline BCVA letter count as a covariate. Least-squares means (LSMeans) for each treatment group, the LSMean difference between each dose of the KVD001 Injection group and the sham procedure group, the corresponding confidence intervals (CIs) and the p-values will be presented.
 
The primary analysis [REDACTED] in the FAS population at the Week 16 visit, as described in Section 8.2.
 
As a sensitivity analysis, treatment group differences for changes from baseline in BCVA letter count will be evaluated using a mixed model repeated measures (MMRM) ANCOVA fitted with treatment group, visit and the treatment by visit interaction as categorical variable terms with baseline BCVA letter score and baseline CST as covariates with contrasts included for each visit. LSMean and 95% confidence intervals for each treatment group, the LSMean difference between each dose of the KVD001 Injection and the sham, the corresponding confidence intervals, and the p-values will be presented for each visit.
 
Secondary Efficacy Analyses:
 
Change from baseline in BCVA letter count in the study eye at Week 24 and change from baseline in CST in the study eye as measured by SD-OCT at Week 16 and Week 24 will be analyzed, separately, using the same method described for the primary efficacy analysis.

--	--

	
The proportion of study eyes with improvement of 2 or more steps from baseline on the ETDRS DRSS score between the sham procedure group and each of the KVD001 Injection groups will be summarized by visit using discrete summary statistics, including 95% asymptotic normal CIs for each treatment group. The difference in proportions between each of the KVD001 Injection groups and the sham procedure group will be analyzed at Week 16 and Week 24 using a Pearson's chi-squared test. The 95% asymptotic normal CIs for the differences in proportions will also be calculated. Fisher's exact tests and exact CIs will be employed in cases of expected counts <5.
 
The proportion of study eyes with ≥ 5, ≥ 10 and ≥ 15 BCVA letter change from baseline (gain and loss) at Weeks 16 and 24 will be analyzed using the same method described for the proportion of study eyes with improvement of 2 or more steps from baseline on the ETDRS DRSS score.
 
Safety Variables:
 
AEs will be coded using the MedDRA dictionary. Frequencies and percentages of subjects with treatment-emergent adverse events (TEAEs), serious TEAEs and TEAEs causing premature discontinuation will be provided by treatment group. An AE is treatment emergent if it occurs or worsens after the first dose of randomized study treatment. Furthermore, frequencies will be given of subjects with TEAEs by system organ class (SOC) and preferred term (PT); by SOC, PT and maximal severity; by SOC, PT and strongest relationship; by SOC and PT for SAEs; and by SOC, PT and day of onset. Separate analyses will be performed for ocular specific and all AEs (including systemic).
 
Other safety endpoints including manifest refraction/BCVA, slit lamp biomicroscopy, dilated ophthalmoscopy, IOP, SD-OCT, ETDRS DRSS, physical exam findings, laboratory test results, and vital signs will be summarized by treatment group and visit using descriptive statistics. Changes or shifts from baseline will also be summarized where appropriate. For assessments performed by eye, study eye and fellow eye will be summarized separately.

--	---

LIST OF STUDY PERSONNEL

Sponsor

KalVista Pharmaceuticals, Ltd.
[name]
[name]
[name]
United Kingdom

[Redacted]
[Redacted]
[Redacted]
[Redacted]
[Redacted]
[Redacted]
[Redacted]
[Redacted]

Contract Research Organization

Ora, Inc.
[name]
[name]
USA

[Redacted]
[Redacted]
[Redacted]
[Redacted]

Adverse Event Reporting

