1 INTRODUCTION AND BACKGROUND

Diabetic macular edema (DME) is a common complication of diabetes mellitus (GS, N et al. 2017). It leads to vision loss, if untreated, and becomes increasingly prevalent with progressing diabetes. In 2015, over 30 million Americans were estimated to be affected by diabetes and almost 10 million by diabetic retinopathy; 1.5M were estimated to have vision-threatening diabetic retinopathy and 908,000 of these would have DME (Lee, Wong et al. 2015). DME is the leading cause of moderate vision loss among working age adults in most developed countries (Diabetes, Complications Trial/Epidemiology of Diabetes et al. 2009).

The clinical signs of diabetic retinopathy begin with retinal hemorrhages and micro-aneurysms, usually associated with areas of retinal pericyte loss and loss of the endothelial cell barrier function (GS, N et al. 2017). The resulting leakage can lead to macular edema, consisting of an accumulation of fluid and lipoproteins in the retina. Visual acuity declines dramatically when the central macula is affected.

Therapies directed against the vascular endothelial growth factor (anti-VEGF therapies) have made a significant difference in the treatment of DME (Campochiaro, Aiello et al. 2016). The treatments currently in use, aflibercept, bevacizumab and ranibizumab, were shown in clinical trials to be more effective than laser therapy after one year. While laser therapy is expected to improve vision by 3 or more lines in one in 10 people with DME, about three in 10 people are expected to gain vision with anti-VEGF treatment: risk ratio (RR) versus laser 3.66 (95% CI: 2.79 to 4.79) for aflibercept; 2.47 (95% CI 1.81 to 3.37) for bevacizumab; 2.76 (95% CI 2.12 to 3.59) for ranibizumab (Virgili, Parravano et al. 2017). However, a significant proportion (up to 50%) of patients with DME does not achieve vision gain under anti-VEGF therapy (Nguyen, Brown et al. 2012).

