8 STATISTICAL METHODS

The statistical considerations summarized in this section outline the plan for data analysis of this study.

Before unmasking, a separate statistical analysis plan (SAP) will be finalized, providing detailed methods for the analyses outlined below.

Any deviations from the planned analyses will be described and justified in the final integrated study report.

Subjects will be randomized by the IRT in a 1:1:1 ratio to 1 of the 3 treatment groups: KVD001 Injection (6 µg/eye or 3 µg/eye) or sham. Allocation to the treatments will be stratified by baseline BCVA (≤ 55 letters vs > 55 letters) and CST at Screening (≤ 450 µm vs > 450 µm) as determined by the study center.

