8.2 General Considerations

All statistical tests will be two-sided and will be performed at the 5% level of significance, unless otherwise stated.

Continuous data will be summarized by treatment group using descriptive statistics (number, arithmetic mean, median, standard deviation [SD], minimum, and maximum). Categorical data will be summarized by treatment group using frequency tables (frequencies and percentages).

All analyses will be carried out using SAS Version 9.4 or higher or using other validated software.

Analysis and data conventions:

Definition of baseline

The baseline assessment will be the latest, valid pre-dose assessment available.

Visit windows

Assessments taken outside of protocol allowable windows will be displayed according to the case report form (CRF) assessment recorded by the Investigator.

Unscheduled assessments

Extra assessments (laboratory data or vital signs associated with non-protocol clinical visits or obtained in the course of investigating or managing AEs) will be included in listings, but not summaries. If more than one laboratory value is available for a given visit, the first valid observation will be used in summaries and all observations will be presented in listings. It is noted that invalid laboratory data may not be used (from hemolyzed samples, mishandled samples, quantity not sufficient, or other conditions that would render values invalid).

Unit of Analysis

Ophthalmic safety endpoints will be analyzed for both eyes. Non-ophthalmic safety endpoints will be analyzed with subject as the unit of analysis. For efficacy endpoints, the unit of analysis will be the study eye.

Missing data conventions

In general, data will not be imputed for safety analysis. The primary and secondary efficacy data analyses will be performed on the FAS [REDACTED]. An analysis using observed data only will also be performed in both the FAS and PPS. Additionally, [REDACTED] the FAS for the analysis of the primary and secondary efficacy variables. No exploratory efficacy endpoints or safety endpoints will be imputed. Additional details will be provided in the SAP.

Multiplicity Considerations

No multiplicity adjustments are planned in this exploratory Phase 2a study.

Other considerations

Since central randomization will be used, no testing for treatment by center interaction will be conducted. No multiplicity adjustments are planned.

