8.5.2 Secondary Efficacy Analyses

The secondary efficacy endpoints are:

- Change from baseline in CST as measured by Spectral Domain OCT (SD-OCT)
- Proportion of eyes with a ≥ 2 step improvement from baseline in DRSS score
- Change from baseline in BCVA letter count as measured by ETDRS
- Proportion of study eyes with ≥ 5 , ≥ 10 , and ≥ 15 BCVA letter change from baseline (gain and loss).

Change from baseline in BCVA letter count in the study eye at Week 24 and change from baseline in CST in the study eye as measured by SD-OCT at Week 16 and Week 24 will be analyzed using the same method described for the primary efficacy analysis. Note that change from baseline in CST will be in favor of KVD001 if the treatment difference is < 0 .

The proportion of study eyes with improvement of 2 or more steps on the ETDRS DRSS score between the sham procedure group and each of the KVD001 injection groups will be summarized by visit using discrete summary statistics, including 95% asymptotic normal CIs for each treatment group. The difference in proportions between each of the KVD001 groups and the sham procedure group will be analyzed at Week 16 and Week 24 using a Pearson's chi-squared test. 95% asymptotic normal CIs for the differences in proportions will also be calculated. Fisher's exact tests and exact CIs will be employed in cases of expected counts < 5 .

The proportion of study eyes with ≥ 5 , ≥ 10 and ≥ 15 BCVA letter change (gain and loss) between baseline and Weeks 16 and 24 will be analyzed using the same method described for the proportion of study eyes with improvement of 2 or more steps on the ETDRS DRSS score.

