8.8 Determination of Sample Size

The proposed sample size (41 per treatment group) will provide approximately 80% power to detect a difference in change from baseline of 5 letters between either of the KVD001 treatment groups and sham based on a two-sided, two-sample t-test with significance level 0.05 and assuming a pooled SD of 7.5 letters.

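### For sparse binary secondary endpoints, Boschloo's test would be a cheap and slightly more powerful small-count fallback than Fisher's exact test (minor)

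*Protocol*

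**What the plan says.** Protocol 8.5.2 compares each dose with sham on two kinds of proportion: eyes improving by 2 or more DRSS steps, and eyes gaining or losing at least 5, 10 or 15 letters. The default is Pearson's chi-squared test, with one exception, which the protocol synopsis states in the same words: "Fisher's exact tests and exact CIs will be employed in cases of expected counts <5".

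SAP 13.3 keeps it, adds the comparison between the two doses, and applies the letter-change analyses at every post-baseline visit. SAP section 1 says that its methods supersede those of the protocol, so SAP 13.3 governs.

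On the level, Protocol 8.2 states: "All statistical tests will be two-sided and will be performed at the 5% level of significance, unless otherwise stated". SAP 8.4 also sets 0.05 two-sided for efficacy. Neither document makes a multiplicity adjustment, and both call the study exploratory. Neither gives an expected event rate, a power figure or a type I error figure for any binary endpoint.

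**The concern.** Fisher's test conditions on the total number of events. When that total is small, only a few p-values are possible, and the largest one at or below 0.05 may lie well under it. The test then rejects much less often than the declared 5%.

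Unconditional exact tests also hold the 5% level but waste less of it, and Boschloo's test is never less powerful than Fisher's. At stake is whether a real difference in a sparse outcome is reported as not significant when an equally valid exact test would detect it. That applies to a 15-letter loss as much as to a 15-letter gain.

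**Working it through.** **The plan's own figure.** There is none for these endpoints. The only power statement is for the primary endpoint: "The proposed sample size (41 per treatment group) will provide approximately 80% power to detect a difference in change from baseline of 5 letters", "assuming a pooled SD of 7.5 letters". A two-sample t-test on those inputs gives 84.7%, and 80% would need 37 per arm. An unstated attrition of about 10% would account for 41 (36.3/0.9 = 40.3, rounded up). None of this affects the present point; only the 41 per arm carries over.

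**Inputs.**
- 41 per arm (Protocol 8.8).
- Equal allocation (Protocol section 8: "Subjects will be randomized by the IRT in a 1:1:1 ratio to 1 of the 3 treatment groups"), so each comparison is 41 v 41.
- Two-sided 5% level (Protocol 8.2).
- Assumed sham event rates of 2%, 5% and 10%.
- The rule is read as applying when any cell's expected count is below 5.

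**Step 1: when the fallback applies.** With t events in the two arms together, the expected number per arm is t/2. This is 4.5 at t = 9 and 5 at t = 10. So Fisher's test is used at 9 or fewer pooled events (9/82 = 11%), or at 9 or fewer non-events.

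**Step 2: what Fisher's test rejects there.**
- 5 v 0: p = 2·C(41,5)/C(82,5) = 2 × 749,398/27,285,336 = 0.055.
- 7 v 1: p = 2·[41·C(41,7) + C(41,8)]/C(82,8) = 0.057.
- 6 v 0: p = 0.026. 8 v 1: p = 0.029.

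With 9 or fewer events, the only rejecting tables are 6 v 0, 7 v 0, 8 v 0, 9 v 0 and 8 v 1, in either direction.

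**Step 3: true type I error of the plan's rule.** This is the sum of Bin(a; 41, p)·Bin(b; 41, p) over those of the 42 × 42 tables (a, b) that the rule rejects.

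| Event rate in both arms | True type I error |
|---|---|
| 2% | 0.01% |
| 5% | 0.47% |
| 7.5% | 1.45% |
| 10% | 2.77% |

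The fallback is used in 99% of null trials at a 5% rate and in 70% at 10%.

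**Step 4: replace only the fallback.** Boschloo's test takes Fisher's p-value as its statistic and maximises the tail probability over the common event rate. It gives p = 0.035 at both 5 v 0 and 7 v 1. Those two tables and their mirrors are the only ones where the verdict changes. Every table that the plan rejects is still rejected. Type I error becomes 0.12% at a 2% rate and 1.5% at 5%.

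**Step 5: power, with Pearson's test kept as default.**

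| Sham v active (assumed) | Plan | Boschloo fallback | Gain (points) | Barnard fallback |
|---|---|---|---|---|
| 2% v 12% | 21.9% | 33.9% | 12.0 | 42.0% |
| 2% v 15% | 39.9% | 52.7% | 12.8 | 58.2% |
| 5% v 15% | 23.5% | 29.5% | 6.0 | 31.1% |
| 5% v 20% | 50.1% | 54.9% | 4.8 | 55.4% |
| 10% v 25% | 43.9% | 44.4% | 0.5 | 44.4% |

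Hand check of the first row: the gain is P(0 | 2%)·P(5 | 12%) + P(1 | 2%)·P(7 | 12%) = 0.4368 × 0.1871 + 0.3655 × 0.1044 = 0.0817 + 0.0381 = 0.120. The reverse tables add almost nothing.

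**Step 6: maximum size.** Over all common event rates, the plan's rule peaks at 5.98%, at a rate of 50%, where Pearson's test is in use. The modified rule has the same maximum. Within the fallback branch, the null rejection probability with Boschloo's test peaks at 2.4%.

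**The case against.** The case for leaving the rule alone is substantial.

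- **Fisher's test is not an error.** It is prespecified and holds its level; its only fault is conservatism. A reader might infer from a 0.5% true size that the analysis is invalid. The documents do not support that.
- **The gain rests on two tables.** At 5 v 0 and 7 v 1 Fisher gives 0.055 and 0.057. SAP 8.4 reports p-values to four decimals, so an attentive reader of an exploratory study learns nearly the same either way.
- **Rarity is assumed.** The nearest figure in the documents, in the protocol's introduction, is that "laser therapy is expected to improve vision by 3 or more lines in one in 10 people with DME". It concerns an active treatment. From a 10% control rate the gain is about 1 point or less.
- **Many tests, no adjustment.** SAP 13.3 allows up to 7 endpoints × 3 comparisons × 6 visits = 126 tests. Some conservatism with sparse events is defensible there.
- **Boschloo's test is also conservative** at low event rates (1.5% at a 5% rate).

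All of this stands, and it limits the point to a minor improvement. It does not remove the point, because the replacement loses no rejection at 41 v 41 and leaves the maximum size unchanged.

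**Conclusion.** The point holds as a cheap, minor improvement. Under the plan's rule, tests of sparse endpoints run well below their declared 5%, and a Boschloo fallback recovers part of the lost power. The gain is about 12 to 13 points at an assumed 2% sham rate, 5 to 6 points at 5%, and almost nothing at 10% or more.

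Three stronger readings are not supported:
- **That a 12-point or larger loss goes with the 0.5% type I error.** The two belong to different assumed rates: 0.5% is the size at a 5% rate, while the larger loss needs a sham rate near 2%. A loss of about 20 points (2% v 12%) arises only against Barnard's test.
- **That these endpoints are shown to be rare.** The documents give no event rates for this population.
- **That the change secures 5% overall.** That guarantee covers the fallback branch only. The combined rule still reaches 6.0% through Pearson's test, as it does now.

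The calculations assume 41 evaluable eyes per arm. With fewer, the tables that change would differ. The sample size and the primary BCVA analysis are unaffected.

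**What to change.** In SAP 13.3, keep Pearson's chi-squared test and replace Fisher's test with Boschloo's unconditional exact test when any expected count is below 5. Record this in SAP section 16, and bring Protocol 8.5.2 and the synopsis into line if the protocol is amended. Settle it before unmasking.

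Name one test only. Barnard's test gains more at very low rates, but it disagrees with Boschloo's at 4 v 0, so leaving both open would allow a choice after seeing the data.

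The cost is one phrase, slightly more programming and validation, and a test name that some readers will not know. SAP section 18.1 shows that the interval method in 13.3 has already been revised once, so an edit of this size is routine.
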